Secondary hypothesis: Group-based sleep intervention with light therapy at gradually advanced timing reduce symptoms in a range of areas including fatigue, sleep, attention deficits, dysfunctional beliefs about sleep and improve well-being, attention, and daytime function significantly more than treatment as usual while on a waitlist for non-pharmacological sleep-treatment in groups (TAU + WL).

The use of bb-glasses enhances the effect of the group-based treatment for DSWPD on SOL.

Figure 1. Overview of the project and the two WPs.

WL= Wait list. TAU=treatment as usual, bb-glasses=Blue-blocking glasses

Two randomized controlled trials (RCTs) will be undertaken in order to obtain an evidence-based treatment model in psychiatric outpatient care for patients with moderate to severe mental illness and comorbid sleep disorders (insomnia and DSWPD).

Choice of method: We have chosen to use the gold standard for experimental trials, RCT, as the methodological design for WP1 and 2. We want to conduct a naturalistic, yet controlled study that is generalizable to common clinical practice and outpatient psychiatric clinics. Hence, the participants will already be patients at an outpatient clinic and are not to be recruited from outside the clinic (such as from the general population). We use an RCT design to avoid confounding biases and in order to be as sure as we can that the intervention in the experimental condition represents the only difference between the groups we study. Most studies on sleep disorders exclude moderate to severe mental illness hence leaving the research results not generalizable to the patient group that may benefit from sleep interventions the most leaving a large knowledge gap regarding these patient groups. In this project, however, that is the specific

group we want to recruit and investigate, and we seek to close this gap concerning the effects of evidence-based treatment studies for sleep disorders. Since we are investigating a tormented and vulnerable group of patients that traditionally have low daytime function and tend to receive welfare, we find it particularly important to have user representatives as part of the project group to speak for the patients.

Inclusion and exclusion criteria for WP 1 and 2:

Inclusion criteria:

- Patients referred to, are offered, and who accepts attendance at the sleep-school at Bjørgvin DPS psychiatric hospital (BDPS)

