Power analysis was conducted with G*Power, version 3.1.9.2 [15]. Relevant effect sizes (Hedges g) for power analyses were based on a recent meta-analysis of randomized controlled trials aiming at improving sleep, but that also reported an impact on mental health. The meta-analysis reported (following the removal of outliers) a large pooled effect size ($g = 0.97$) on sleep quality. The pooled effect size for composite mental health outcomes was $g = 0.42$ [16]. Another relevant meta-analysis on the effects of CBTi in patients with mental disorders and comorbid insomnia showed that effect sizes (Hedges g) for reduction of insomnia severity post-treatment were 0.50 for patients with depression, 1.50 for patients with PTSD, 1.40 for patients with alcohol dependency, 1.20 for patients with psychosis/bipolar disorder, and 0.80 for patients with mixed comorbidities, respectively. Effects on mental health symptom severity post-treatment were 0.50 for depression, 1.30 for PTSD, 0.90 for alcohol dependency (only one study), 0.30 for psychosis/bipolar, and 0.80 for mixed comorbidities [17]. Against this background an assumed effect size (Cohens d) for insomnia symptoms (primary outcome) of 0.80 was expected, whereas an expected effect size of 0.40 was deemed reasonable for the secondary (mental health) outcomes. Analyzing the data using ANOVA, setting the alpha to .05, power ($1 - \beta$) set to .80, and the correlation coefficient between repeated measures to $r = .50$, showed that 16 patients are needed to detect significant time (pre-post) x group (treatment vs. wait-list) interaction effects. In terms of the secondary outcomes ($d = 0.40$), a similar power analysis showed that a total of 52 patients are required. Taking into consideration an attrition rate of 10%, we aim, based on this power analysis, to recruit a total of 60 patients. For the sub-sample in the treatment group using additive bb-glasses, we base our power calculation on a study reporting ES of 1.6 [18]. Following the same procedure as above, we need 6 participants to show a significant time (pre-post) x group (standard care vs. treatment) interaction.

Power analysis for the DSWPD RCT

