Randomization procedures: Randomization was performed by: <https://www.randomizer.org/> before inclusion. When a new patient is referred to the sleep team and meets the inclusion criteria evaluated in an individual pre-consultation before the group-based sleep-school, the patient is asked if they want to participate in the study. If they say yes, they are assigned either to Sleep-school or waitlist while in treatment as usual (TAU + WL) based on a pre-defined list. All receive a date the Sleep-school starts without being told whether or not they are assigned to a wait-list condition. They are also assigned a date for data collection at two time-points. For the Sleep-school group this is before (T1) and after (T2) Sleep-school, while for those in the TAU + WL condition are assigned T1 and T2 at least 8 (WP1) or 6 (WP2) weeks apart before they start the Sleep-school. Hence, blinding is not completely ensured, but not overt. Wait-list for specific treatments in psychiatric care is normal.

Stability in the treatment in the Sleep-school: The content (slides, hand-outs, video material) and the plan for each session in the sleep-school remains the same throughout the project. The structure has been tested over 4 years before we started recruiting and hence it is well tested. [name] and [name] has lead these groups together as co-therapists since 2017 and plan to continue until 2026 and onwards. In case of sick-leave or other unexpected circumstances, there are colleagues who can fill in for the sleep team. To ensure that the included patients receives the same treatment, we will not change the content or the structure of the sleep-school as long as we are collecting data for these projects. TAU will naturally vary with different therapists. This study is a naturalistic study in a clinic as it is, which will increase generalizability of our research.

Risks: In terms of risks and risk-mitigation table 1 below presents an overview

Table 1: Risk and risk-mitigation related to the project

Risk	Probability	Severity	Mitigating action
Problems recruiting patients	Low	High	If occurring, advertising to increase recruitment is possible and multi-sites may be established in Helse-Bergen.
Equipment malfunction	Medium	Medium	Continuously ensure data quality. Have stand-by replacement equipment
Unequal gender balance	Medium	Medium	Take this into account in the analyses and analyze for gender differences.

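### T1 is a post-allocation baseline, and the start date given before it could let a patient guess the arm; completing T1 first is a cheap improvement

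*Protocol*

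**What the plan says.** The sequence is in Protocol section 1.3, Randomization procedures. The list is generated before inclusion. Eligibility is judged at an individual pre-consultation, and the patient is then asked to take part. Of those who agree, the protocol says: "they are assigned either to Sleep-school or waitlist while in treatment as usual (TAU + WL) based on a pre-defined list". Next: "All receive a date the Sleep-school starts without being told whether or not they are assigned to a wait-list condition". Then: "They are also assigned a date for data collection at two time-points".

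The assessment dates follow different rules in the two arms. The first rule reads: "For the Sleep-school group this is before (T1) and after (T2) Sleep-school". The second rule covers the other arm: "while for those in the TAU + WL condition are assigned T1 and T2 at least 8 (WP1) or 6 (WP2) weeks apart". Both wait-list assessments are placed ahead of the course. The protocol draws its own conclusion: "Hence, blinding is not completely ensured, but not overt".

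Three other places bear on the point:

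- Section 1.2 describes it as clinic routine to give a start date after the pre-consultation.
- Section 1.3, Choice of method, justifies randomisation so that "the intervention in the experimental condition represents the only difference between the groups we study".
- The power analysis for the insomnia RCT "showed that 16 patients are needed to detect significant time (pre-post) x group (treatment vs. wait-list) interaction effects"; the DSWPD power analysis uses the same contrast.

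**The concern.** A baseline is safest when it is recorded before anyone can know or guess the arm. Any difference between arms at that point is then due to chance. Here T1 comes after allocation, and the patient already holds a start date. A distant start suggests the wait-list. If the T2 date is also known, its position relative to the start says more: T2 follows the course in the Sleep-school arm and precedes it in TAU + WL.

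All seven WP1 primary outcomes are self-reported: ISI, BIS, SOL, WASO and SE from diaries, BDI-II and BAI. In WP2 the same is true of BDI-II, BAI and the diary measures, but not of DLMO or actigraphy. A patient who expects to wait may answer these measures differently from one who expects to start soon. That difference would arise after randomisation, so randomisation would not balance it, and it would pass straight into a pre-post x group comparison.

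**Working it through.** **Step 1: order of events, as written.** Pre-consultation and eligibility; consent; arm from the list; start date received; T1 and T2 dates assigned by an arm-dependent rule; T1. The T1/T2 rule cannot be applied until the arm is known, so T1 follows allocation in both arms. No outcome assessment is described between consent and allocation. The BDI and BAI scores at referral appear only in the inclusion criteria.

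**Step 2: what the patient can see.** Patients receive the start date. They are assigned the T1 and T2 dates, and the text does not say when the T2 date is communicated. The date orders are T1, start, T2 (Sleep-school) and T1, T2, start (TAU + WL). The full order is visible before T1 only if the T2 date has been communicated by then.

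**Step 3: the plan's own figures.** With f = d/2, lambda = f² x N x 2/(1 - r), r = .50, alpha .05 and an F test on 1 and N - 2 df:

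- d = 0.80, N = 16: lambda = 0.16 x 16 x 4 = 10.24, power 0.845.
- d = 0.40, N = 52: lambda = 0.04 x 52 x 4 = 8.32, power 0.808.
- d = 0.60, N = 24: lambda = 0.09 x 24 x 4 = 8.64, power 0.802.
- Attrition: 52/0.90 = 57.8, so 58, within the target of 60.

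The stated sample sizes reproduce, and none of them depends on when T1 is taken.

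**Step 4: what a T1 shift would do, if there were one.** Inputs from the protocol: 60 patients less 10% = 54 completers, and r = .50. Assumptions: 1:1 allocation (27 per arm), no true effect, and a shift s in one arm at T1 only. The documents give no value for s; 0.05, 0.10 and 0.20 SD are chosen to show a range.

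- Change score: SD of change = sqrt(2(1 - .50)) = 1.00 SD; SE = sqrt(2/27) = 0.272 SD; the contrast moves by s; noncentral t, 52 df.
- Baseline-adjusted: the contrast moves by r x s; residual SD = sqrt(1 - .25) = 0.866; SE = 0.866 x 0.272 = 0.236 SD; 51 df.

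| s (SD) | s/0.40 | s/0.80 | Two-sided error, change | Two-sided error, adjusted |
|---|---|---|---|---|
| 0.05 | 12.5% | 6.25% | 5.4% | 5.1% |
| 0.10 | 25% | 12.5% | 6.5% | 5.5% |
| 0.20 | 50% | 25% | 11.1% | 7.0% |

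The ratio columns read the planned d as a between-arm difference in change, in units of the SD of a single measurement. Almost all of the 11.1% lies in one tail (10.8% against 0.4%, rounded), so whether it favours or penalises treatment depends on the unknown direction of the shift.

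**Step 5: a different assumption.** If a patient who guesses the arm shifts by the same amount at T1 and T2, the change contrast moves by s - s = 0 under the present order. With T1 completed before any guess is possible, the T2 shift alone would remain and the contrast would move by s. Equal persistence is no better supported by the documents than a T1-only shift.

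**The case against.** The strongest reply is that the protocol withholds the arm, openly admits that concealment is incomplete, and follows ordinary clinic practice in giving a start date. Waiting for a specific treatment is described as normal, so a start date by itself may tell the patient little. The text does not say that the T2 date reaches the patient before T1. All of this stands, and it limits the claim to what a patient could guess.

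The error rates rest on shifts that have no source in the documents, and Step 5 shows that one plausible pattern cancels under the present order. Baseline adjustment, which a statistical analysis plan may specify, would hold the largest listed case to 7.0%. These points also stand. The table is therefore an illustration and not an estimate.

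A reader might infer that the baseline is biased, that patients are in effect told their arm, or that the order of dates is itself a design error. The documents support none of these. The arm is not disclosed, no T1 imbalance is reported, and the different position of the course relative to T2 is inherent in a wait-list comparison.

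What remains is that T1 follows allocation when it need not. Open self-report at T2 cannot be avoided in this design; exposure of T1 can. A T1 taken first is a baseline that allocation cannot have influenced, whatever happens later.

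**Conclusion.** The point holds as a cheap improvement of procedure. T1 is a post-allocation baseline for largely self-reported outcomes, and the start date, with the T2 date if it is given then, could suggest the arm before T1 is answered. That T1 follows allocation comes directly from the text; that the T2 date is known before T1 is an inference.

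No bias is shown, and its size and direction are unknown. Under a T1-only shift, 0.05 SD would be negligible and 0.20 SD would not. Sample sizes are unaffected. The objective WP2 measures are less exposed than the questionnaires and diaries.

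A separate, minor wording point: Randomization procedures gives the wait-list spacing of T1 and T2 as a minimum, while Ethical considerations has treatment start directly after a fixed 6 or 8 weeks of waiting. The two should be reconciled. This review does not say which is right.

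**What to change.** For patients still to be enrolled:

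- Complete T1, at least the questionnaires and the sleep diary, after consent and before the list entry is opened. Set the start and T2 dates only then.
- If the clinic must schedule earlier, withhold the start and T2 dates from the patient until T1 is complete.
- State in Randomization procedures when patients learn each date.

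For all patients, report the T1-T2 interval by arm. Align the waiting-time wording of Randomization procedures and Ethical considerations.

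Costs: patients get shorter notice, and scheduling is slightly later than under the section 1.2 routine, because the diary has to be finished first. The baseline procedure changes mid-trial, so the date of change must be recorded. Self-report at T2 stays open. No extra patients are needed.

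The change reaches only future enrolments. The latest count given is 23 + 14 = 37 of 120 patients at 9 June 2023, with recruitment scheduled to end on 31.10.25 (WP1) and 30.06.26 (WP2). If a work-package has closed, only the reporting and wording items apply, and the order of T1 and allocation should be stated as a limitation.

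Comparing the change from referral to T1 by arm on BDI and BAI would not replace the fix. With 30 per arm and r = .50 assumed, its 95% half-width is 2.002 x sqrt(2/30) = 0.517 SD, and its power against 0.20 SD is about 12%.

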2.1. Potential impact of the proposed research

When the project is completed, we have a vast amount of new knowledge that can be used in optimizing treatment at BDPS and other DPS's nationally and similar outpatient clinics internationally. If the results from this project show that a group-based sleep school over 6 / 8 weeks improves not only sleep measures but also psychiatric symptoms, reduce medication use and reduces the length of treatment, we will manualize the treatment and train therapists to become sleep school leaders based on the protocol and organization used in this project, hence manualizing this model. With the knowledge obtained from this project, it might be possible to tailor treatment and offer it to those who most likely will benefit from it. Hence, this project can potentially increase the effectiveness of the treatment in psychiatric health care.

In the field of psychiatry, the results from this project might be of great importance because sleep disorders in many cases are an obstacle to other treatment (the client has DSWPD and sleeps from 8 am to 16 pm, making attendance to therapy sessions difficult or a patient with comorbid insomnia cannot benefit from psychotherapy because of issues with fatigue and attention). One-on-one talk therapy can be very time-consuming and if this project shows significant improvement also in psychiatric symptoms, patients and therapists can be saved from many time-consuming treatments that otherwise may not be very successful. The treatment in this project may in some cases be all the patient needs, work as a pre-treatment before other protocols (i.e. trauma-treatment) and in some cases be adjacent to individual therapy, enhancing its effects.

2.1 Potential for societal impact of the research project (optional)

This project has the potential to address the UN sustainable goal number 3: Good health and well-being. Sleep problems are common and can be treated relatively quickly, hence SIP has the potential to target good health and well-being wherever the treatment is implemented.

2.2. Measures for communication and exploitation

Communication with other stakeholders: Summaries of results and interpretations with interest for a wider audience will be disseminated in appropriate outlets (e.g., the web pages at the University of Bergen and Helse-Bergen). In addition, the findings will be communicated to user groups, policymakers, and practitioners within medical and mental health services through lectures and the media, as well as the general public. The project group has a long experience in cooperation with national media channels and public outreach that will allow us to implement an effective communication and dissemination plan for this project. Throughout the project, preliminary results will be presented at national and international research conferences.

Scientific results: Results will be published in internationally acknowledged peer-reviewed open-access journals within medicine, psychiatry, and psychology. We expect to publish at least 8 international publications based on the findings from the current project within the project period. Working titles for the articles are:

1. Comorbid insomnia and moderate to severe psychiatric illness: A treatment protocol for a naturalistic, randomized controlled trial (manuscript is almost ready as first draft)
2. Comorbid delayed sleep-wake phase disorder and moderate to severe psychiatric illness: A treatment protocol for a naturalistic, randomized controlled trial
3. Group-based cognitive behavioural therapy for insomnia in a transdiagnostic sample at a psychiatric outpatient clinic: A randomized controlled trial
4. Group-based chronotherapy for delayed sleep-wake phase disorder in a transdiagnostic sample at a psychiatric outpatient clinic: A randomized controlled trial
5. Personality disorders and Delayed sleep-wake phase disorder in a transdiagnostic psychiatric sample
6. Psychophysiological changes after treatment for insomnia in a transdiagnostic psychiatric sample
7. Executive functions and attention deficits in patients with sleep disorders comorbid to psychiatric illness
8. Changes in work attendance after treatment for sleep disorders comorbid to psychiatric illness

3. Implementation

3.2 Project organisation and management

Work plan and tasks: Recruitment, data collection, scoring, plotting and analysis of data, writing, critically reviewing, submitting articles, and disseminating results will take place between the last quarter of 2021 and the last quarter of 2026 (see details in Gantt chart below). Dissemination will likely extend further than 2026. Patients are referred to the sleep school at BDPS where [name] and [name] are on-site. Data-collection is done continuously as patients are recruited to participate in the study. Because of the slow-open group-treatment, this is possible to follow up continuously. Five patients have already been to their 12-month follow up data collection. [name] and [name] assign full days every two-three months to score and plot data, hence some data have already been plotted. We will continue doing this throughout the study period when feasible.

Preliminary data: As of January 2023 we did preliminary analysis where we tested Cohens' d on the first 9 participants in WP1. We found large effect sizes (ES) of 1.9 for insomnia symptoms (ISI), 1.34 for sleep efficiency (SE) and medium (0.53, 0.79 and 0.72) for total sleep time, depression and anxiety in the Sleep-school group, while in the TAU + WL group the ES were negative (-0.28) for total sleep time, and low to medium (0.57, 0.12, 0.22 and 0.29) respectively for the same variables.

Gantt chart:

Table 1. Gantt shows the project management for SIP

	TASK NAME	START DATE	END DATE	Task performed by project group member(s)	2024				2025				2026				
					Q1	Q2	Q3	Q4	Q1	Q2	Q3	Q4	Q1	Q2	Q3	Q4	
Work-package 1																	
Recruitment	15.12.21	31.10.25	[name], [name]														
Data collection	15.12.21	31.12.25	[name], [name], BO														
Scoring, plotting, analyze data	14.02.21	30.04.26	[name], [name], BO														KD
Write, critically review and submit articles	01.01.23	31.12.26	All project group members														
Disseminate results	01.10.26	31.12.26	[name], BO														
Work-package 2																	
Recruitment	20.06.22	30.06.26	[name], [name]														
Data collection	20.06.22	30.06.26	[name], [name], BO														
Scoring, plotting, analyze data	20.08.22	30.06.26	[name], [name], BO														KD
Write, critically review and submit articles	03.03.24	31.12.26	All project group members														
Disseminate results	01.10.26	31.12.26	[name], BO														
Milestones																	
Seminary for the project group		12.01.24	All project group members														
Seminary mid-evaluation		11.01.25	All project group members														
Seminary for the project group		10.01.26	All project group members														
WP1 data collection completed for RCT		31.12.25	[name], [name], BO														
WP2 data collection completed for RCT		30.06.26	[name], [name], BO														

Key Deliveries (KD): data listings for statistical analysis finalized

Probability of recruiting enough patients within the time frame: As of June 9th 2023 we have recruited 23 patients to WP 1 (recruitment started December 15th 2021) and 14 patients to WP2 (recruitment started June 20th 2022). With the current pace of recruitment, we will have recruited 60 patients for WP1 by the end of 2025 and 60 patients for WP2 by the third quarter of 2026. Referrals to the sleep-school has increased by over 30% in 2023 compared to corresponding timeline in 2022. We have not made any attempt to increase recruitment to the studies, we only recruit from patients being referred as part of clinical practice. It is possible to do more to recruit referrals if we find it necessary later on. We will do an evaluation of this by the end of 2024.

Resources:

3. Project manager [name] will lead both WPs; 2024-2026 in a 100% position. BDPS funds this as of now but free purchase from clinical duties besides the Sleep team is warranted in order to complete the projects as planned.
4. Research assistant [name] will work 20% on this project with WP1 and 2 over 3 years; 2024-2026. She will keep her clinical position at BDPS. Her Master thesis will be based on SIP.
5. BO can use some of his assistant professor position at UoB for data collection, analysis of data, writing, critically reviewing, submitting articles, and disseminating results.

6. The rest of the project group will be consulted and will take part in the project as described as part of their existing jobs with no funding from this proposal.
7. We aim to supervise psychology students who are writing their master thesis on topics related to these projects and that will provide more resources when it comes to scoring and plotting the data, as well as literature searches, and in some cases possibly also in the writing the scientific articles. Several project members hold positions at the UoB, hence access to students is ensured.

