1.3. Research questions and hypotheses, theoretical approach and methodology

We will test the following hypotheses in two work-packages (WPs):

1. An RCT with 60 psychiatric outpatients with comorbid insomnia and moderate to severe mental illness to investigate the positive impacts of an additive group-based treatment for insomnia compared to treatment as usual in psychiatric care while on a wait-list for non-pharmacological sleep-treatment in groups.
2. An RCT with 60 outpatients with comorbid DSWPD and moderate to severe mental illness to investigate the positive impacts of an additive group-based treatment for DSWPD compared to treatment as usual in psychiatric care while on a wait-list for non-pharmacological sleep-treatment in groups.

The specific aims of this project are to test the following hypotheses:

WP 1

Primary hypothesis: Group-based sleep intervention based on CBTi reduces insomnia symptoms and symptoms of anxiety and depression significantly more than treatment as usual while on a waitlist for non-pharmacological sleep-treatment in groups (TAU + WL).

Primary outcome measures: Insomnia Severity Index (ISI), the Bergen Insomnia Scale (BIS), and Sleep Onset latency (SOL), Wake after sleep onset (WASO), and Sleep efficiency (SE) from sleep diaries, Becks Depression Inventory (BDI-II) and Becks Anxiety Inventory (BAI).

Secondary hypothesis: Group-based sleep intervention based on CBTi reduces symptoms in a range of areas including fatigue, sleep, attention deficits, dysfunctional beliefs about sleep, and improves well-being, attention, and daytime function significantly more than treatment as usual while on a waitlist for non-pharmacological sleep-treatment in groups (TAU + WL).

The use of bb-glasses enhances the effect of the group-based treatment for insomnia on SOL.

WP 2

[figure not shown]
Primary hypothesis: Group-based sleep intervention with light therapy at gradually advanced timing advances sleep timing and reduces symptoms of anxiety and depression significantly more than treatment as usual while on a waitlist for non-pharmacological sleep-treatment in groups (TAU + WL).

Primary outcome measures: Measured subjectively and objectively by sleep diaries, Genactiv actigraphy, and saliva samples (intraindividual variation of rise time (IIV), dim light melatonin onset (DLMO), rise /wake up-time), Becks Depression Inventory (BDI-II) and Becks Anxiety Inventory (BAI).

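### The protocol has project members, apparently including Sleep-team staff, score data during recruitment and states no masking of those who derive WP2's actigraphic outcomes and DLMO

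*Protocol*

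**What the plan says.** **Scoring.** Section 3.2 (Work plan and tasks) says that two project members "assign full days every two-three months to score and plot data, hence some data have already been plotted", and that this will continue through the study when feasible. The Gantt chart has a WP2 row "Scoring, plotting, analyze data 20.08.22 30.06.26", staffed by two members whose names are removed and a third given by initials. Under Resources, master's students in psychology are expected too, "that will provide more resources when it comes to scoring and plotting the data".

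**Treatment and recruitment.** Section 1.3 (Stability in the treatment in the Sleep-school) says of the two group leaders that the pair "has lead these groups together as co-therapists since 2017 and plan to continue until 2026 and onwards". The Gantt recruitment rows list two members. Under Resources, the project manager leads both work packages, and "free purchase from clinical duties besides the Sleep team is warranted in order to complete the projects as planned". The Budget paragraph asks for the project leader and a research assistant to be released from clinical posts, partly to manage data while recruitment runs.

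**Allocation and blinding.** After the individual pre-consultation, consenting patients enter the trial and "they are assigned either to Sleep-school or waitlist while in treatment as usual (TAU + WL) based on a pre-defined list". Patients get a Sleep-school start date without being told whether they are on the wait-list. Then comes the only statement on blinding: "Hence, blinding is not completely ensured, but not overt".

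**Outcomes.** The WP2 sleep-timing primary outcomes are "Measured subjectively and objectively by sleep diaries, Genactiv actigraphy, and saliva samples", covering rise time, its intraindividual variation (IIV) and DLMO. BDI-II and BAI are also primary.

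**The concern.** BDI-II, BAI and the sleep diaries are self-report, from patients who may work out their arm. DLMO is the WP2 primary outcome best protected from patient expectation, and actigraphy at least does not depend on what the patient writes down. That protection holds only if the person who turns the raw record into a value cannot be influenced by knowing the arm. Setting a rise time from an actigraphy record, or an onset from a melatonin profile, can involve judgement, and the protocol gives no scoring rule. Section 1.2 describes the treatment model as one the clinic already regards as working, so the team has an expectation about the result.

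If those who treat or recruit also score with the arm in view, the objective outcomes lose much of their value as a check on the self-reports.

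**Working it through.** The point rests on what the protocol assigns to whom, so the check is mainly a side-by-side reading. One figure bears on the weight of DLMO and is reproduced first.

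**1. How much of WP2 rests on DLMO.** Inputs from section 1.3 (Power analysis for the DSWPD RCT): d = 0.60, alpha 0.05, power 0.80, r = 0.50, two groups, two time points. For the time-by-group F test, f = d/2 = 0.30 and λ = N·m·f²/(1 − r) = 24 × 2 × 0.09 / 0.50 = 8.64. With 1 and 22 degrees of freedom the power is 0.802, so the stated 24 is reproduced. For the mental-health outcomes, d = 0.40 gives f = 0.20 and λ = 52 × 2 × 0.04 / 0.50 = 8.32. Power is 0.807 at the stated 52, and 52/0.90 = 57.8, or 58, which fits within the planned 60. DLMO is therefore the basis of the primary calculation (24), while the recruitment target of 60 is set by the mental-health outcomes and attrition.

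**2. Is scoring done in-house while patients are being recruited?** Yes. The WP2 scoring row starts on 20.08.22, two months after WP2 recruitment opened on 20.06.22, and both rows end on 30.06.26.

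**3. Do scoring and treating staff overlap?** The project manager stays in the Sleep team and is to be released to manage data. Two members recruit; two members plus a third score. Names are removed throughout, so overlap is a strong inference for at least part of the team. It cannot be verified person by person.

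**4. Could scorers know the arm?** Whoever leads a group sees who attends. The T1 and T2 schedules also differ by arm: before and after Sleep-school in one, and at least 6 weeks apart ahead of it in the other (WP2). Section 3.2 (Preliminary data) reports effect sizes by arm for the first 9 WP1 participants in January 2023, so outcomes had already been linked to arm during recruitment. That does not show that scoring itself was done with the arm in view.

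**5. Is masking of scorers stated?** No. The blinding sentence follows directly on what patients are told, and scorers are not mentioned there or elsewhere.

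**6. Which outcomes are exposed?** WP1's primary outcomes are ISI, BIS, diary measures, BDI-II and BAI, where scoring leaves little room for judgement. In WP2, DLMO and the actigraphic rise time and IIV are exposed.

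**7. How many files could need re-reading?** WP2 had 14 patients on 9 June 2023. Only some data had been plotted, so 14 is an upper bound at that date. Funding for saliva analysis (261,000 NOK) was still being applied for, so fewer melatonin profiles, or none, may have been available.

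**The case against.** The strongest answer is that the protocol is silent here and does not state anything wrong. The scoring sentence names no outcome. Saliva analysis has its own budget line, and a laboratory may do the assay. A third member, who holds a university post, is listed for scoring, and students are foreseen. Scoring rules and file coding may sit in a data-handling document or an analysis plan that is not at hand. The protocol also says openly that blinding is incomplete.

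Much of this stands. A reader might infer that the co-therapists themselves read DLMO and actigraphy knowing each patient's arm. The document does not support that: the scorers' identities are removed, no one is named as deriving DLMO, and nothing says that files carry the arm when scored. A reader might also extend the point to WP1's primary outcomes, which are questionnaires and diaries, or attach a size to the bias, for which the protocol gives no input. Rise time is moreover patient behaviour, which a motivated patient can change, so the argument is strongest for DLMO.

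What does not stand is leaving the matter to a later analysis plan. Who scores, and what they can see, is trial conduct, and scoring is already under way. An analysis plan cannot mask a file after it has been read.

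**Conclusion.** The concern holds for WP2 in a limited form. The protocol describes in-house scoring during recruitment by project members who apparently include Sleep-team staff, and it states no masking of scorers. That leaves actigraphic rise time and IIV, and DLMO, open to scorer bias. It should be put right, because these are the primary outcomes called objective and DLMO carries the 24-patient calculation.

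The size of any bias cannot be computed from the document. The conclusion rests on two assumptions: that the scorers overlap at least partly with the treating or recruiting staff, and that deriving these values leaves some room for judgement. If a laboratory or an uninvolved member already derives them from coded files under a fixed rule, saying so in the protocol would settle the matter.

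**What to change.** - Export WP2 actigraphy records and saliva melatonin profiles under a random code, without arm, visit or calendar date. Clock time has to stay, since the outcomes are clock times.
- Derive rise time, IIV and DLMO by a fixed written rule.
- Give the scoring to someone already in the plan who did not treat the patient, such as the psychology students or a university project member.
- Lock the values before the code is linked to arm.
- Re-read under code only those WP2 files already scored with the arm known: at most 14 patients as of June 2023, to be recounted at the date of the change.
- State in the protocol who derives each of these outcomes and what they can see.

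The cost is a coding key, some re-reading and slightly slower data handling. No new staff role is needed. Coding cannot hide a marked shift in timing that is visible in the record itself; the written rule is there to limit what a scorer can do with it.
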